**Table 1. Toxicity management for durvalumab and combination radiation therapy**

Toxicity	Action durvalumab	Action radiation therapy
Pneumonitis	As per Table 1	Hold if durvalumab held and/or RT-related toxicity resolved to <Grade 3
Hepatitis	As per Table 1	Hold if durvalumab held and/or RT-related toxicity resolved to <Grade 3
Colitis	As per Table 1	Hold if durvalumab held and/or RT-related toxicity resolved to <Grade 3
Diarrhea	As per Table 1	Hold if durvalumab held and/or RT-related toxicity resolved to <Grade 3
Pancreatitis	As per Table 1	Hold if durvalumab held and/or RT-related toxicity resolved to <Grade 3

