### **6.5.2 Radiation therapy toxicity evaluation and management**

Acute radiation toxicities are those that occur within 90 days from therapy start and will be graded according to CTCAE v4.03. Toxicities related to RT differ based on the location of the treated lesion(s) and are related to dose received by OARs near the targeted lesion. The majority of lesions that receive ER on this study are anticipated to be in the thorax and abdomen based on the patterns of spread of pancreatic cancer. The most common sites of distant metastases are the liver, abdominal peritoneum, and lungs. Accordingly, the most likely potential acute radiation adverse events include fatigue, dermatitis, pneumonitis, esophagitis, colitis, hepatitis, nausea, vomiting, anorexia, and diarrhea.

RT should be continued without interruption, if possible. Grade 3 or higher acute toxicity from RT is not expected and is not expected to lead to RT interruption. However, Grade 3 or higher acute toxicity may necessitate a treatment break. If a treatment delay for acute toxicity is required, the total radiation dose and dose per fraction will not be modified. Any missed radiation fractions should be made up as quickly as possible; if needing to give RT and durvalumab on the same day then the RT should be given first, if possible. It should be noted that any Grade 3-5 acute radiation toxicity counts toward the early stopping rule.

Patients will be evaluated by a radiation oncologist at least once weekly during RT (Weeks 2 and 4) for physical examination and toxicity evaluation. Patients will be seen at least every 4 weeks by a radiation oncologist or medical oncologist thereafter starting in Week 8.

Late toxicities are those that occur after 90 days of therapy start and will be graded according to CTCAE v4.03. Late toxicities, like acute toxicities, are related to dose received by OARs near the targeted lesion.

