### **6.5.3 Toxicity management guidelines for combination treatment regimen**

Acute toxicity attributable to RT and not durvalumab should be managed accordingly with optimal supportive care measures. If toxicity clearly related to RT and not durvalumab  $\geq$  Grade 3 is persistent, then a RT break is allowable until the toxicity decreased to  $<$  Grade 3. Durvalumab should be continued during the RT break provided that there are no documented toxicities from durvalumab that would necessitate holding durvalumab. If durvalumab is held due to toxicity attributed solely to the durvalumab, then the RT should also be held until durvalumab is resumed. Once durvalumab is resumed, RT should also be resumed.

In addition to the individual toxicity management guidelines for durvalumab and RT described above, Table 4 outlines what actions are recommended for the management of any potential overlapping toxicities that may occur following treatment with this combination (e.g., which agent should be modified first, etc.).

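### The RT-action column of the Section 6.5.3 toxicity table makes recovery to below Grade 3 a reason to hold RT, the reverse of the section's text

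*Combined protocol and SAP*

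**What the plan says.** Section 6.5.3 ends with a table of recommended actions for toxicities that durvalumab and RT may both cause. It is printed as Table 1 and cited in the text as Table 4. Its rows are pneumonitis, hepatitis, colitis, diarrhea and pancreatitis. The radiation column has the same entry in each: "Hold if durvalumab held and/or RT-related toxicity resolved to <Grade 3".

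The paragraph above the table sets three rules.

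- Toxicity due to RT: "If toxicity clearly related to RT and not durvalumab" is Grade 3 or higher and persistent, "a RT break is allowable until the toxicity decreased to" below Grade 3.
- Durvalumab during that break: "Durvalumab should be continued during the RT break provided that there are no documented toxicities from durvalumab that would necessitate holding durvalumab".
- Toxicity due to durvalumab: "If durvalumab is held due to toxicity attributed solely to the durvalumab, then the RT should also be held until durvalumab is resumed".

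Section 6.5.2 says "Grade 3 or higher acute toxicity from RT is not expected and is not expected to lead to RT interruption", and then that "Grade 3 or higher acute toxicity may necessitate a treatment break". It gives no end point for the break. It also states that "any Grade 3-5 acute radiation toxicity counts toward the early stopping rule".

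**The concern.** In the table entry, the word if governs both conditions. Its second half therefore tells staff to hold RT once RT-related toxicity has come down below Grade 3, and it says nothing about holding while the toxicity is Grade 3 or worse. In the text, severity starts the break and recovery ends it. The table has recovery starting the hold.

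The table is the action summary for toxicities shared by the two treatments, so staff may consult it without reading the paragraph above. Section 6.5.2 names pneumonitis, colitis, hepatitis and diarrhea, four of the five rows, among the likeliest acute RT effects. Followed literally, the entry would allow treatment through severe RT toxicity and withhold it after recovery.

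**Working it through.** No figure in the plan depends on this entry, so the main check is a comparison of texts.

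| Situation | Section 6.5.3 text | Table entry as printed |
|---|---|---|
| Durvalumab held for its own toxicity | Hold RT until durvalumab resumes | Hold RT (agrees) |
| Persistent Grade 3+ toxicity clearly due to RT, durvalumab continuing | RT break allowed | No hold given |
| The same toxicity, now below Grade 3 | Break ends | Hold RT |

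The last two rows conflict. The durvalumab-held condition does not cover them, because the text continues durvalumab during an RT-only break unless a separate durvalumab toxicity requires a hold. Section 6.5.2 supports the text on what starts a break. The wording is complete and identical in 5 of 5 rows, so a fault in reading the PDF is unlikely.

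**When the entry could matter.** RT is given on Days 15-17 and Days 29-31 (Section 5.2.2).

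- Fractions per patient: 2 × 3 = 6.
- Each course takes three consecutive days, which leaves little room for persistent toxicity to interrupt a course under way. The realistic decision is whether to start the second course.
- Gap between courses: 29 − 17 = 12 days.
- Share of fractions in the second course: 3/6 = 50%.
- Planned fractions: 39 × 6 = 234, with 39 patients from Section 11.3.

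**How many patients.** The documents give no rate for Grade 3 or higher toxicity attributed to RT before Day 29 with durvalumab continuing. The rates below are assumptions. The top value, 10%, is the design rate in Section 11.2.1 for all Grade 3 or higher acute non-hematologic toxicity, so it should overstate this subset.

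| Assumed rate | Patients (39 × rate) | Second-course fractions (× 3) | Share of 234 |
|---|---|---|---|
| 1% | 0.39 | 1.17 | 0.5% |
| 5% | 1.95 | 5.85 | 2.5% |
| 10% | 3.9 | 11.7 | 5.0% |

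These rows count patients for whom the entry would be the relevant line. They do not count patients managed wrongly.

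**Stopping rule.** Section 6.5.2 counts Grade 3-5 acute radiation toxicity whether or not RT is held. The change in boundary counts is 0, and no input to the sample size changes.

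**The case against.** The strongest reply is that nobody would act on the literal wording. The instruction makes no clinical sense, and the usable rule stands in full sentences directly above the table. Section 5.2.5 requires make-up fractions to allow time off for significant toxicity, and Section 6.5.2 has a radiation oncologist see patients at least weekly during RT. This is persuasive about the size of the effect. It does not make the entry correct: the reader has to override the table with the text.

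A second reply is scope. The table covers overlapping toxicities and supplements the separate guidance for each treatment. Section 10.2.2 accepts that attribution may be impossible, and Table 1 of Section 6.5.1 treats events without a clear alternative cause as potentially immune related. For Grade 3 or higher pneumonitis, diarrhea or hepatitis, that table then holds or stops durvalumab, so the correct half of the entry would often govern. That stands, and it narrows the gap. It does not close it, because the entry itself names RT-related toxicity and is wrong on that.

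Third, the patient counts rest on assumed rates, and harm also requires a clinician to follow the printed words against the text. Both points are right. The counts are an upper range for relevance, not an estimate of harm.

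Last, the entry's first half is broader than the text, which ties the RT hold to toxicity attributed solely to durvalumab. That difference is on the cautious side and is separate from the inversion.

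**Conclusion.** The inconsistency is real and minor. In all five rows, the condition on RT-related toxicity is inverted relative to the text of Section 6.5.3. The conflict arises only when Grade 3 or higher toxicity is attributed to RT and durvalumab is not held, and in practice it bears on starting the second course. On assumed rates of 1% to 10%, that is about 0.4 to 3.9 of 39 patients. Section 6.5.2 does not expect such toxicity, and a treating radiation oncologist would probably recognise the slip. The primary endpoint, power, sample size and stopping boundary are unaffected. That a missing until is the cause is an inference; the contradiction does not depend on it.

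**What to change.** Replace the radiation entry in all five rows with:

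*Hold RT while durvalumab is held; RT may also be held for persistent RT-related toxicity ≥Grade 3 until it resolves to <Grade 3.*

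This keeps the RT-toxicity break optional, as in the text. To match the text more closely, the second clause could say clearly related to RT and not durvalumab. The cost is one phrase repeated in five rows, with no design or statistical change; it can go into the next amendment.

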## **7. RESTRICTIONS DURING THE STUDY AND CONCOMITANT TREATMENT(S)**

### **7.1 Restrictions during the study**

#### **Contraception**

Females of childbearing potential who are sexually active with a nonsterilised male partner must use 2 methods of effective contraception from screening, and must agree to continue using such precautions for 90 days after the final dose of investigational product, or for at least 90 days following the last infusion of Durvalumab; cessation of birth control after this point should be discussed with a responsible physician. Periodic abstinence, the rhythm method, and the withdrawal method are not acceptable methods of birth control.

- Females of childbearing potential are defined as those who are not surgically sterile (i.e., bilateral tubal ligation, bilateral oophorectomy, or complete hysterectomy) or postmenopausal (defined as 12 months with no menses without an alternative medical cause).
- Subjects must use 2 acceptable methods of effective contraception as described in Table 5.
- Nonsterilised males who are sexually active with a female partner of childbearing potential must use 2 acceptable methods of effective contraception (see Table 5) from Day 1 and for 90 days after receipt of the final dose of investigational product.

**Table 2. Effective methods of contraception (two methods must be used)**

Barrier Methods	Intrauterine Device Methods	Hormonal Methods
Male condom plus spermicide	Copper T	Implants
Cap plus spermicide	Progesterone T a	Hormone shot or injection
Diaphragm plus spermicide	Levonorgestrel-releasing intrauterine system (e.g., Mirena ® ) a	Combined pill Minipill Patch

a This is also considered a hormonal method.

### **Blood donation**

Subjects should not donate blood while participating in this study or for at least 90 days following the last infusion of durvalumab.

### **Diet**

Subjects should maintain their usual diet. No dietary modification is required with the exception of those required to manage an AE such as diarrhea.

## **7.2 Concomitant treatment(s)**

### **7.2.1 Permitted concomitant medications**

Investigators may prescribe concomitant medications or treatments (e.g., acetaminophen, diphenhydramine) deemed necessary to provide adequate prophylactic or supportive care except for those medications identified as “excluded” as listed in Section 7.2.2.

All concomitant medication will be recorded in the electronic study database including all prescription, over-the-counter, herbal supplement, and IV medications. If changes occur during the trial period, documentation of drug dosage, frequency, route, and date may also be included in the electronic study database.

All concomitant medications received within 30 days before the first dose of trial treatment and 30 days after the last dose of trial treatment should be recorded. Concomitant medications administered after 30 days after the last dose of trial treatment should be recorded for SAEs.

### **7.2.2 Excluded Concomitant Medications**

The following medications are considered exclusionary during the study.

1. Any investigational anticancer therapy other than the protocol specified therapies.
2. Any concurrent chemotherapy, radiotherapy (except palliative radiotherapy), immunotherapy, biologic or hormonal therapy for cancer treatment. Concurrent use of hormones for noncancer-related conditions (e.g., insulin for diabetes and hormone replacement therapy) is acceptable. Local surgical treatment of isolated lesions for palliative intent is acceptable. Palliative RT in addition to what is intended to be given on this study is strongly discouraged, especially prior to imaging assessment after 8 weeks of study therapy. The treating physician should determine whether additional RT is clinically indicated and whether other alternative management options are available. The treating physician should also assess whether additional RT would be well tolerated, taking into account prior radiation dose to OARs.
3. Immunosuppressive medications including, but not limited to systemic corticosteroids at doses not exceeding 10 mg/day of prednisone or equivalent, methotrexate, azathioprine, and TNF- $\alpha$  blockers. Use of immunosuppressive medications for the management of investigational product-related AEs or in subjects with contrast allergies is acceptable. In addition, use of inhaled and intranasal corticosteroids is permitted. A temporary period of steroids will be allowed for different indications, at the discretion of the principal investigator (e.g., chronic obstructive pulmonary disease, radiation, nausea, etc).
4. Live attenuated vaccines within 30 days of durvalumab dosing (i.e., 30 days prior to the first dose, during treatment with durvalumab and for 30 days post discontinuation of durvalumab. Inactivated vaccines, such as the injectable influenza vaccine, are permitted.

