## **4.2 Exclusion criteria**

Subjects should not enter the study if any of the following exclusion criteria are fulfilled:

1. Involvement in the planning and/or conduct of the study (applies to both AstraZeneca staff and/or staff at the study site)
2. Previous enrolment in the present study
3. Any previous treatment with a PD1 or PD-L1 inhibitor, including durvalumab
4. Prior RT to any lesion that would receive RT on this protocol.
5. Prior RT that could lead to an unacceptably high risk of clinically significant normal tissue injury due to high cumulative normal tissue dose as determined by the investigator.
6. Subjects who have received second-line or later chemotherapy for metastatic pancreatic cancer (prior chemotherapy received in the non-metastatic setting does not count).
7. History of another primary malignancy except for:
  - Malignancy treated with curative intent and with no known active disease  $\geq 3$  years before the first dose of study drug and of low potential risk for recurrence
  - Adequately treated non-melanoma skin cancer or lentigo maligna without evidence of disease
  - Adequately treated carcinoma in situ without evidence of disease e.g., cervical cancer in situ

8. Receipt of the last dose of anti-cancer therapy (chemotherapy, immunotherapy, endocrine therapy, targeted therapy, biologic therapy, tumor embolization, monoclonal antibodies, other investigational agent)  $\leq 14$  days prior to the first dose of study drug.
9. Mean QT interval corrected for heart rate (QTc)  $\geq 470$  ms calculated from 3 electrocardiograms (ECGs) using Fridericia's Correction
10. Current or prior use of immunosuppressive medication within 28 days before the first dose of durvalumab, with the exceptions of intranasal and inhaled corticosteroids or systemic corticosteroids at physiological doses, which are not to exceed 10 mg/day of prednisone, or an equivalent corticosteroid
11. Any unresolved toxicity ( $>$ grade 2, CTCAE version 4.03) from previous anti-cancer therapy. Subjects with irreversible toxicity that is not reasonably expected to be exacerbated by the investigational product may be included (e.g., hearing loss, peripherally neuropathy).
12. Any prior Grade  $\geq 3$  immune-related adverse event (irAE) while receiving any previous immunotherapy agent, or any unresolved irAE  $>$ Grade 1

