### Specific Immune-mediated Reactions

Adverse Events	Severity Grade of the Event (NCI CTCAE version 4.03)	Dose Modifications	Toxicity Management
			
 
- If TSH < 0.5 × LLN, or TSH >2 × ULN or consistently out of range in 2 subsequent measurements, include free T4 at subsequent cycles as clinically indicated and consider endocrinology consult.
 

	Grade 2	
For Grade 2 endocrinopathy other than hypothyroidism, hold study drug/study regimen dose until patient is clinically stable.
 
 
• If toxicity worsens, then treat as Grade 3 or Grade 4.
 
 
Study drug/study regimen can be resumed once event stabilizes and after completion of steroid taper.
 
Patients with endocrinopathies who may require prolonged or continued steroid replacement can be retreated with study drug/study regimen on the following conditions:
 
 
1. The event stabilizes and is controlled.
 
2. The patient is clinically stable as per investigator or treating physician’s clinical judgement.
 
3. Doses of prednisone are ≤10 mg/day or equivalent.
 
	
For Grade 2 (including those with symptomatic endocrinopathy):
 
 
- Isolated hypothyroidism may be treated with replacement therapy without treatment interruption and without corticosteroids.
 
- Initiate hormone replacement as needed for management.
 
- Evaluate endocrine function, and as clinically indicated, consider pituitary scan.
 
- For patients with abnormal endocrine work up, except for those with isolated hypothyroidism, consider short-term corticosteroids (eg, 1 to 2 mg/kg/day methylprednisolone or IV equivalent) and prompt initiation of treatment with relevant hormone replacement (eg, levothyroxine, hydrocortisone, or sex hormones).
 
- Once the patient is improving, gradually taper steroids over ≥28 days and consider prophylactic antibiotics, antifungals, and anti-PCP treatment (refer to current NCCN guidelines for treatment of cancer-related infections [Category 2B recommendation]).a
 
- For patients with normal endocrine workup (laboratory assessment or MRI scans), repeat laboratory assessments/MRI as clinically indicated.
 

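### Section 7.2.2 item 3 bars on study the low-dose systemic steroids (up to 10 mg/day prednisone) on which exclusion criterion 10 lets patients enter

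*Combined protocol and SAP*

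**What the plan says.** **On-study rule.** Section 7.2.2 lists treatments that are not allowed during the study. Item 3 covers immunosuppressive drugs in an open-ended list, and its first example is "systemic corticosteroids at doses not exceeding 10 mg/day of prednisone or equivalent". Methotrexate, azathioprine and TNF-alpha blockers follow. Section 7.2.1 gives the list its force: investigators may give concomitant treatments "deemed necessary to provide adequate prophylactic or supportive care except for those medications identified as" excluded in Section 7.2.2.

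**Entry rule.** Exclusion criterion 10 in Section 4.2 concerns "Current or prior use of immunosuppressive medication within 28 days before the first dose of durvalumab". It makes an exception for intranasal and inhaled steroids and for "systemic corticosteroids at physiological doses, which are not to exceed 10 mg/day of prednisone, or an equivalent corticosteroid". The synopsis prints the same criterion.

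**Exceptions to the on-study rule.** Item 3 states: "Use of immunosuppressive medications for the management of investigational product-related AEs or in subjects with contrast allergies is acceptable". It permits inhaled and intranasal steroids, and it adds: "A temporary period of steroids will be allowed for different indications, at the discretion of the principal investigator". Item 2 of the same list states: "Concurrent use of hormones for noncancer-related conditions (e.g., insulin for diabetes and hormone replacement therapy) is acceptable".

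**The concern.** An on-study restriction on immunosuppressants would normally bar steroid doses above a physiological ceiling and tolerate doses below it, as criterion 10 does. Item 3 uses the same ceiling but attaches the prohibition to doses at or below it. A patient who enters properly on such a dose is therefore outside the prescribing rules from then on.

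What is at stake is trial conduct. Sites have to follow the list in Section 7.2.2. Taken literally, it requires a validly enrolled patient on long-term low-dose steroids either to stop them or to be treated in breach of the protocol. Section 7.2.1 requires all concomitant medication to be recorded, so such use would be visible in the study database.

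**Working it through.** The protocol gives no figure to reproduce on this point. The check is a comparison of the provisions, followed by a rough count under a stated assumption.

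**1. The provisions side by side**

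| Provision | Period covered | Treatment of systemic steroids at or below 10 mg/day prednisone |
|---|---|---|
| Section 4.2, criterion 10 (also in the synopsis) | Up to the first durvalumab dose, including current use | Exempt from the exclusion |
| Section 7.2.2, item 3 | On study | Named as excluded |
| Section 6.5.1, Table 1 (durvalumab toxicity management) | On study, after an immune-related event | Compatible with durvalumab |

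Because criterion 10 covers current use, a patient can be on an exempt dose on the day of first dosing. Item 3 applies from that point. The synopsis repeats criterion 10 and does not add a second rule, so there is one operative conflict.

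**2. Which direction was intended**

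Table 1 in Section 6.5.1 requires permanent discontinuation if steroids cannot be reduced to 10 mg/day or less within 12 weeks. For endocrinopathy needing continued steroid replacement, one condition for retreatment is: "Doses of prednisone are ≤10 mg/day or equivalent". These entries show that low doses were regarded as acceptable alongside durvalumab. They do not themselves conflict with item 3, because item 3 exempts treatment of product-related adverse events.

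**3. Whether high doses slip through**

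They do not. The list in item 3 is open-ended, so immunosuppressive doses above 10 mg/day remain excluded. The error is over-exclusion of low doses only.

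**4. Whether the exceptions close the gap**

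- Product-related adverse events and contrast allergy: these do not cover steroids the patient was already taking for another reason.
- Inhaled and intranasal use: not systemic.
- Temporary use at the principal investigator's discretion: does not plainly cover continuing use.
- Hormone replacement (item 2): may cover adrenal replacement, although corticosteroids are not named there.

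Chronic, non-replacement use at or below 10 mg/day is left over. Criterion 13, which excludes most autoimmune disease active or documented in the past 2 years, makes that group smaller still.

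**5. How many patients**

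The documents give no prevalence. Assume that a proportion p of the 39 planned patients is in the remaining group. Then the expected number is 39p, and the chance of at least one such patient is 1 − (1 − p)^39.

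| p (assumed) | Expected number, 39p | Chance of at least one |
|---|---|---|
| 0% | 0 | 0% |
| 1% | 0.39 | 32.4% |
| 2% | 0.78 | 54.5% |
| 5% | 1.95 | 86.5% |

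**6. Effect on the analysis**

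Section 11.2.2 specifies strict intention-to-treat analysis. The PFS definition in Section 11.4 has no censoring tied to concomitant medication. Neither the primary analysis nor the sample size in Section 11.3 depends on item 3.

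**The case against.** The strongest reply is that the two rules govern different periods. A stricter on-study rule is not in itself a contradiction, since a patient could enter on a low dose and then taper. That would be coherent if the protocol described a taper, but it does not. On the literal reading item 3 also excludes both low and high doses, which leaves the 10 mg figure with no function. An inverted phrase is the more plausible explanation.

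A second reply is that almost nobody is affected. Criterion 10 speaks of physiological doses, which may largely mean replacement, and item 2 accepts hormone replacement. The discretion clause in item 3 sets no dose cap or maximum duration and gives chronic obstructive pulmonary disease as an example. Durvalumab lasts at most 12 months (Section 5.1.2) and the target median PFS is 4.5 months (Section 11.3), so an investigator could stretch the clause to many cases. This stands as a limit on the size of the problem. It does not remove the conflict: criterion 10 limits the dose but does not require a replacement indication, and a temporary period is not indefinite use.

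Third, the protocol does not spell out the consequence. Section 4.3 does not list use of an excluded medication as such among the reasons for stopping durvalumab, and no rule classes it as a deviation. That is correct. Stopping the steroid or recording a breach is what one would expect under a binding list, but it is an inference.

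Finally, the assumed prevalence range has no basis in the documents, and the resulting chances of at least one patient run from 0% to 86.5%. They illustrate scale and should carry no more weight than that.

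**Conclusion.** The concern holds as a minor wording error in an operative rule. No other provision in the protocol corrects it. The practical reach is probably few or none of the 39 patients; that judgement rests on the narrowness of the remaining group, because the protocol supplies no count. Confidence is high that the phrase is inverted, and much lower that any patient would be harmed or any deviation recorded because of it.

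**What to change.** In Section 7.2.2 item 3, change *not exceeding* to *exceeding*, so that systemic corticosteroids are barred on study only above 10 mg/day of prednisone or equivalent. This brings the on-study rule into line with exclusion criterion 10 and with the toxicity table. Leave the existing exceptions in items 2 and 3 as they are. The cost is a one-phrase amendment, which can go in with the next protocol revision at the latest; design, sample size and analysis do not change.
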